4.2 Trial

The study is a cRCT in 60 pharmacies. Fifteen pharmacies will be assigned to each of the four study arms: 3 involving pharmacy-delivered PrEP/PEP services (Arms 1-3) and 1 SOC (Arm 4). These pharmacies will have at least 20 months to enroll participants, **Figure 1**, with the option to extend this longer if needed to achieve target sample size.

Figure 1. Overview of study implementation activities over duration of the cRCT.

4.3 Intervention

Implementation of the intervention will begin with training of pharmacists, pharmaceutical technologists, and HTS counselors who will be involved in the delivery of PrEP/PEP and associated counseling and HIV testing services. This will culminate in an observed practice session. Throughout the study, research assistants will visit the pharmacies to monitor activities and provide support.

4.4 Randomization

4.4.1 Randomization design

Stratified permuted block randomization will be performed to ensure balance by key prognostic covariates in the first stage of the randomization. Specifically, the goal is to achieve balance across the 4 arms by county or county group (4 counties/county groups, each with 15 participating pharmacies plus 5 back-up pharmacies). Randomization will proceed as shown in **Table 1**, which describes the number of pharmacies that will be in each arm by county.

Of note, implementation was originally planned in 2 counties in Western Kenya (e.g., Kisumu and Homa Bay), this was expanded to 2 additional neighboring counties to ensure the pharmacies selected for study participation were spaced far enough away from one another and an ongoing cRCT in the region testing different models of pharmacy-delivered PrEP services for adolescent girls and young women seeking contraception (i.e., to prevent potential contamination).

This randomization strategy results in balance of treatment assignment by county/county group (in each county/county group, 3-4 pharmacies are in each of the 4 arms) and overall (15 pharmacies assigned to each arm). Within each of these stratified blocks, treatment assignment can be permuted. For instance, consider the 20 urban pharmacies in Kiambu County. Three of these will be assigned to Arm 1, 4 will be assigned to each of Arms 2-4, and 5 will be assigned as back-up pharmacies; the arm assignments will be randomized within this block. Note that by pursuing a stratified randomization scheme, analyses must adjust for county/county group (categorical). In addition to determining which arm a given pharmacy is in, it is necessary to determine whether it will be designated as a cRCT pharmacy or a back-up pharmacy.

Table 1: Randomization scheme for the cRCT and back-up distribution.

County	Arm 1	Arm 2	Arm 3	Arm 4	Back-up pool	Total # pharmacies
Kiambu	3	4	4	4	5	15 cRCT + 5 back-up
Nairobi	4	4	3	4	5	15 cRCT + 5 back-up
Kisumu/Siaya	4	3	4	4	5	15 cRCT + 5 back-up
Homa Bay/Migori	4	4	4	3	5	15 cRCT + 5 back-up
TOTAL	15	15	15	15	20	60 cRCT + 20 back-up

4.4.2 Randomization process

Each pharmacy will select an opaque envelope at the end of the training session; the contents of the envelope will indicate which arm the pharmacy is randomized to or if it will be a back-up pharmacy. The training will be done by county. For the county groups, whatever envelopes are not selected at the first training will be available for selection at the second training. Thus, the following envelopes are proposed:

Kiambu County: Arm 1 envelopes: n = 3; Arm 2 envelopes, n = 4; Arm 3 envelopes, n = 4; Arm 4 envelopes: n = 4; back-up pharmacy envelopes: n = 5

Nairobi County: Arm 1 envelopes: n = 4; Arm 2 envelopes, n = 3; Arm 3 envelopes, n = 4; Arm 4 envelopes: n = 4; back-up pharmacy envelopes: n = 5

Kisumu/Siaya Counties: Arm 1 envelopes: n = 4; Arm 2 envelopes, n = 4; Arm 3 envelopes, n = 3; Arm 4 envelopes: n = 4; back-up pharmacy envelopes: n = 5

Homa Bay/Migori Counties: Arm 1 envelopes: n = 4; Arm 2 envelopes, n = 3; Arm 3 envelopes, n = 4; Arm 4 envelopes: n = 3; back-up pharmacy envelopes: n = 5

4.4.3 Replacement of dropped pharmacies

During implementation, it is anticipated that some participating pharmacies may have to drop from or be dropped from the study (by the research team) for a variety of reasons, including provider/ownership turnover, inability to follow study procedures, request of pharmacy provider, a gap in service delivery (>1 month), etc. In these instances, these pharmacies will be replaced with one from the pool of back-up pharmacies for each county/county group. When replacement is needed, a pharmacy from this back-up pool will be randomly selected. The back-up pool will ideally not drop below 2-3 pharmacies, with backup pharmacies identified and trained as needed.

4.5 Sample size and power

We had planned to analyze the PrEP and PEP initiation and continuation outcomes as binary outcomes, using an individual-level analysis. However, in September 2023, it became apparent that the denominators that would be used in these estimates (number enrolled) would vary greatly across arms (and indeed would be affected by which arm a pharmacy was randomized to) and would likely lead to biased estimates of the proportions initiating/continuing in each arm. In particular, the intervention is thought to (a) have an effect on likelihood of enrollment and (b) have an effect on likelihood of PrEP/PEP initiation (and thus continuation); we would like to capture the total effect of the intervention, i.e., both (a) and (b). However, by only considering individuals who were enrolled (which corresponds to the previous analytic approach), we would only capture (b), and would be ignoring (a).

Thus, we are instead pursuing a cluster-level analysis of the initiation and continuation outcomes, where each cluster (pharmacy) is summarized by the number of initiations/continuations over the course of the study, accounting for pharmacy size (i.e., pharmacy flow). This is reflected in the analytic approach described below.

The anticipated number of PrEP and PEP initiations and continuations within 60 days of pharmacy screening per pharmacy in each study arm over 16 months of implementation are given in **Table 2**. Estimates of the total counts per pharmacy in each arm were based on those observed in pilot studies of pharmacy-delivered PrEP and PEP services: (1) one which offered PrEP for a fee of 350 KES in 4 pharmacies—informing Arm 1 PrEP initiation and continuation estimates (Ortblad et al., J Int AIDS Soc. 2023), and (2) another which offered PrEP and PEP services for free in 12 pharmacies—informing Arm 2 PrEP initiation and continuations estimates, as well as PEP initiation and continuation estimates (Roche et al., CROI 2023). The estimates in other arms were based on the hypothesized difference between the arms—with the hypothesis that Arm 3 (implementor-sustained with HTS counselor support) would perform best, followed by Arm 2 (implementor-sustained), Arm 1 (clients-sustained), and Arm 4 (SOC referral). The PrEP continuation estimates in Arm 4 (SOC referral) were additionally informed by the Partners Scale-up Project, with delivered PrEP services in 24 public clinics in Kenya. Based

on the hypothesized number of PrEP/PEP initiations, proportion of PrEP initiators who would continue PrEP, and proportion of PEP users who would transition to PrEP (“PEP continuation”), the number of PrEP/PEP continuations was determined.

Table 2: Hypothesized number of pharmacy-based PrEP, PEP, and PrEP/PEP initiations and continuations per pharmacy (k=60) and arm, based on pilot and implementation studies

Study arms:	1: Client-sustained	2: Implementor-sustained	3: HTS-supported	4: Referral (SOC)
PrEP initiations : over 16 months (monthly)	128 (8 monthly)	176 (11 monthly)	208 (13 monthly)	80 (5 monthly)
PrEP continuations : over 16 months (% of initiators)	64 (50% initiators)	123 (70% initiators)	166 (80% initiators)	48 (60% initiators)
PEP initiations : over 16 months (monthly)	32 (2 monthly)	48 (3 monthly)	64 (4 monthly)	16 (1 monthly)
PEP continuations : over 16 months (% of initiators)	4.34 (14% initiators)	9.12 (20% initiators)	13.90 (23% initiators)	2.61 (17% initiators)
PrEP/PEP initiations : over 16 months	160	224	270	96
PrEP/PEP continuations : over 16 months	68.34	132.12	179.90	50.61

The numbers in Table 2 were originally used to estimate power, yielding power of nearly 100% for the comparison of each direct pharmacy delivery arm (Arms 1-3) to Arm 4 (SOC). However, in Fall 2024, it became apparent that far more individuals were initiating PEP as opposed to PrEP, and the target number of PrEP initiations was not feasible. Given the very high power in the original design, the PrEP initiation numbers in Table 2 were scaled such that the power for PrEP initiations (one of the primary outcomes) for the smallest comparison—Arm 1 (client-sustained) vs. Arm 4 (SOC)—was 80%. This would thus guarantee power >80% for the comparisons of Arms 2 and 3 vs. Arm 4 (**Table 3**). The estimated power for each comparison is then given in **Table 4**.

In particular, to estimate power, it was assumed that the average pharmacy flow was the same across the four arms; there is no a priori reason to assume otherwise. We further assumed a coefficient of variation (CV) of 0.25. The coefficient of variation characterizes the variability in number of PrEP initiations (relative to pharmacy size) across pharmacies. While this is difficult to know ahead of time, it is typically <0.25 (Hayes and Bennett, *IJE*, 1999). A CV of 0.25 would roughly correspond to a situation where, for example, the average number of PrEP initiations was 20/pharmacy, and 95% of pharmacies had between 10 and 30 initiations (assuming equal flow across pharmacies); this seems to be a reasonable degree of variability in our setting. Given that the analyses will include comparisons of Arms 1, 2, and 3 vs. 4, we used a Bonferroni correction to our alpha level (two-sided alpha = 0.05/3) for the PrEP 60-day initiation/continuation outcomes and the combined PrEP/PEP outcomes (primary and key secondary outcomes).

Based on the hypothesized number of PrEP/PEP initiations and continuations in **Table 3**, we estimated the power would be very high for comparing Arms 2 and 3 to Arm 4 for PrEP initiation

and continuation (primary outcomes) and the combined PrEP/PEP initiation and continuation outcomes (key secondary outcomes; **Table 4**). For the Arm 1 vs. Arm 4 comparisons, the power is estimated to be 80% for PrEP initiation (as designed), 100% for the combined PrEP/PEP initiation outcome, and lower for the continuation outcomes.

→ **Primary outcome assessment will be completed after a total of 1,119 PrEP initiations are achieved. A study duration of 20 months of implementation is targeted.**

Table 3: Number of PrEP, PEP, and PrEP/PEP initiations and continuations per pharmacy (k=15/arm, k=60 total) for >80% power in our PrEP outcomes of interest

	1: Client-sustained	2: Implementor-sustained	3: HTS supported	4: Referral (SOC)	TOTAL (across 60 pharms)
PrEP initiations	16.13	22.18	26.21	10.08	1,119
PEP initiations	32	48	64	16	2,400
Total PrEP/PEP initiations	48.13	70.18	90.21	26.08	3,519
PrEP continuations	8.06 (50% of initiations)	15.52 (70% of initiations)	20.97 (80% of initiations)	6.05 (60% of initiations)	759
PEP continuations	4.34 (13.6% of initiations)	9.12 (19.0% of initiations)	13.90 (21.7% of initiations)	2.61 (16.3% of initiations)	450
Total PrEP/PEP continuations	12.40	24.64	34.87	8.66	1,209

Table 4: Estimated power for PrEP initiation and continuation and the combined PrEP/PEP initiation and continuation outcomes

	Arm 1 vs. Arm 4	Arm 2 vs. Arm 4	Arm 3 vs. Arm 4
PrEP initiations	80%	100%	100%
PrEP continuations	23%	100%	100%
Total PrEP/PEP initiations	100%	100%	100%
Total PrEP/PEP continuations	48%	100%	100%

Sample sizes for other aspects of the study (e.g., extended surveys, provider surveys, costing data, IDIs), were chosen based on feasibility and ability to obtain a representative sample. The extended client surveys will include 1,340 participants across the four arms. One provider and/or HTS counselor from each pharmacy will be asked to participate in the provider survey at baseline, 60 days, and 270 days post-launch of PrEP/PEP service delivery at their pharmacy. IDIs will be conducted with up to 88 PrEP and 60 PEP candidates (with product candidacy determined by providers at enrollment following an HIV risk assessment, medical safety assessment, and counseling session). We will also interview 40 pharmacy providers, 15 HTS counselors (supporting Arm 3 pharmacies), and the study's remote clinician. IDI sampling will be done using random stratified purposeful sampling, with PrEP client sampling stratified by PrEP

initiation and continuation, PEP client sampling stratified by PEP initiation and PEP-to-PrEP transition, and provider sampling stratified by pharmacy performance (high/low performer based on PrEP initiation rates relative to other pharmacies in the same arm).

In order to achieve our targeted number of PrEP (1,119) and PEP (2,400) initiations, we anticipate needing to enroll 5,865 client participants (1,865 pharmacy PrEP candidates and 4,000 pharmacy PEP candidates). This assumes that 75% of enrolled client participants will complete the brief client survey at 60 days, and of those, 80% will initiate PrEP/PEP. Combining this target with the other types of participants (60 pharmacy providers, 15 HTS counselors, 4 remote clinicians), our total enrollment target is 5,944 participants.

5 Planned Analyses

No formal interim analyses are planned. Data listings and summaries similar to those described here may be provided to the Data Safety and Monitoring Board (DSMB), but statistical testing will not be included. The DSMB was provided with the total number of PrEP initiations per arm and per pharmacy to determine whether enrollment should be extended to 20 months or beyond; this was shared with the DSMB in a closed session partway through implementation. Given relatively low enrollment at this time, it was decided to extend the study to 20 months. Analyses described in this plan are final analyses to be performed on the final dataset for the study.

6 General Statistical Considerations

6.2 Data sources

The following data sources will be used to address the objectives (detailed in **Table 5**):

- Pharmacy records: intervention arms only, Arms 1-3 (i.e., not SOC arm, Arm 4)
 - Items on Prescribing Checklist, including PEP/PrEP dispensing data, age, sex, marital/relationship status, behaviors associated with HIV risk, HIV test result
 - Other services/products purchased
- Clinic records: SOC arm only
 - Items on the Clinical Encounter Form akin to those in the study's Prescribing Checklist
- Brief client surveys: all arms
 - Brief demographics
 - Whether the participant initiated PrEP and/or PEP and, if so, where
 - Whether the participant has refilled PrEP and, if so, where
 - Whether the participant is still taking PrEP/PEP as of today
 - If the participant is still taking PrEP/PEP, how many PrEP/PEP pills they swallowed in the past 7 days
 - PrEP adherence
 - Select HIV risk behavior questions

- Extended client survey: all arms
 - Extended demographics
 - Alcohol use
 - Sexual and mental health
 - HIV risk behaviors
 - Fertility
 - Social harm
 - Acceptability of pharmacy model in which they received PrEP/PEP services
 - Quality of care perceptions Fidelity of services received
 - Willingness to pay
- Provider surveys: all arms
 - Provider demographics
 - Acceptability of pharmacy-delivered PrEP/PEP
 - Feasibility of pharmacy-delivered PrEP/PEP
 - Self-efficacy to delivery PrEP/PEP services at pharmacies
 - Organizational Readiness for Change (ORIC)
 - Willingness to charge
- Client in-depth interviews: all arms
 - Model acceptability
 - Model appropriateness
 - Acceptability of modifications
 - Appropriateness of modifications
- Provider in-depth interviews: all arms
 - Acceptability
 - Feasibility
- Technical assistance (TA) reports
 - Adaptations

Data from the Maisha Meds application on PrEP/PEP delivery/dispensing, survey data, audio files from interviews, and interview transcripts will be stored on secure electronic platforms that meet all data security requirements (e.g., REDCap, Dedoose). Table 5 below summarizes the outcomes and data sources.

Table 5. Data sources

PRIMARY/ SECONDARY	OUTCOME	TIMING	DATA SOURCE
Primary	PrEP initiation	By 60 days	Brief client survey Pharmacy records* Clinic records*
	PrEP continuation	By 60 days	
Secondary	PrEP initiation	By 270 days	
	Any PrEP continuation	By 270 days	
	At least 2 PrEP refills	By 270 days	
	Any stopping and restarting PrEP (i.e., PrEP reinitiation)	By 60 and 270 days	
	PEP initiation	By 60 and 270 days	
	PEP-to-PrEP transition	By 60 and 270 days	
	PrEP-to-PEP transition	By 60 and 270 days	
	Repeat PEP use	By 60 and 270 days	
	PrEP/PEP initiation	By 60 and 270 days	
	PrEP/PEP continuation	By 60 and 270 days	
	PrEP adherence	At 60 days	
			Brief client survey (self-report)
Tertiary	HIV risk behaviors	At 60 and 270 days	Brief client survey Extended client survey
	Follow-up HIV testing	At 60 and 270 days	
	PrEP coverage	Over study duration	Brief client survey Pharmacy records* Clinic records*
	Client: acceptability	At 60 and 270 days	
	Client: quality of care perceptions	At 60 and 270 days	
	Client: willingness to pay	At 60 and 270 days	Extended client survey Client interviews
	Client: fidelity		
	Provider: acceptability	At baseline, 60, and 270 days	
	Provider: feasibility	At baseline, 60, and 270 days	Provider interviews Provider surveys
	Provider: willingness to charge	At baseline, 60, and 270 days	
	Provider: perceived self-efficacy	At baseline, 60, and 270 days	
	Pharmacy: adaptations	Over study duration	TA reports
	Pharmacy: sustainability		Brief client survey Pharmacy records* Clinic records*

*The pharmacy records and client records will be used for comparison of outcomes between intervention arms and other secondary analyses; see Section 7.5 for details.

6.3 Descriptive statistics

Continuous variables and count data will be described with mean (SD) or median (Q1, Q3). Categorical variables will be described with N (%).

6.4 Statistical testing and models

Statistical tests will be 2-sided tests and considered statistically significant if $p < 0.05$ (i.e., $\alpha = 0.05$), with the exception of the analyses of the PrEP initiation and continuation outcomes and the combined PrEP/PEP initiation and continuation outcomes, which constitute the primary and key secondary outcomes. These will utilize a significance threshold of $0.05/3 = 0.0167$ to account for the three comparisons of Arms 1, 2, and 3 versus Arm 4.

6.5 Exposure groups

The exposure groups are the 4 study arms, (determined by randomized group assignment of the clinic) which will be treated as a categorical variable throughout the analyses.

6.6 Analysis populations

- *Cluster-Randomized Control Trial Client Population*
All pharmacy clients enrolled in the cluster-randomized controlled trial phase of the study. Data from these individuals includes data from pharmacy records, clinic records (of referral facilities), and client surveys—including brief surveys among all clients at 60 and 270 days post enrollment, and extensive surveys among select clients at 0, 60, and 270 days post-enrollment.
- *Extended Client Survey Population*
Clients enrolled in the study who were randomly selected and completed the extended client survey.
- *Client Interview Population*
PrEP and PEP clients randomly selected for an in-depth interview.
- *Provider Interview Population*
Pharmacy providers and HTS counselors randomly selected to provide an in-depth interview.
- *Provider Survey Population*
Pharmacy providers and HTS counselors randomly selected to complete the provider survey.
- *Enrolled Pharmacies Population*
All pharmacies included in the study. All pharmacies in the study will contribute pharmacy records for the estimation of costs.
- *Costing Population – Provider, Costing Population – Pharmacy*
One provider from each pharmacy in the Enrolled Pharmacies Population (costing survey) and 10 pharmacies randomly selected from the Enrolled Pharmacies Population (time-in-motion studies).

6.7 Missing values

Missing data in the primary outcomes, i.e., PrEP initiation and continuation, are of greatest concern.

The primary analysis of the PrEP outcomes (described more fully below) will rely on data from the brief client surveys to create uniformity between the intervention arms (for which pharmacy dispensing data will also be available) and the SOC arm (for which clinic dispensing data will also be available). To accommodate missing PrEP outcomes, we will impute missing values as failures (i.e., did not initiate or did not continue, depending upon the outcome under consideration). This same strategy will also be applied to our secondary PrEP/PEP outcomes. Note that since the primary analysis relies on pharmacy-level counts of individuals who initiated/continued PrEP/PEP, for the primary analysis, this imputation procedure will be equivalent to a complete case analysis.

In addition to the analyses above, for the analysis of PrEP initiation at 270 days, we will perform a **sensitivity analysis** where PrEP initiation at 60 days is used to impute missing PrEP initiation at 270 days. For instance, if a participant reports initiating PrEP at 60 days, but PrEP initiation status at 270 days is unavailable, we will consider this participant to have initiated PrEP at 270 days. This would be expected to reduce recall bias in the 270 day outcome.

7 Data Analysis

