- PrEP continuation: the number of participants at each pharmacy that initiated PrEP at the pharmacy or clinic and returned to the pharmacy or clinic and refilled PrEP **within 60 days** of initial pharmacy-based screening. *Comparisons between intervention arms and the control will rely on self-report from the 60-day client survey, while comparisons between intervention arms will employ pharmacy records.*

Secondary outcomes include those related to PrEP initiation, PrEP continuation, PrEP adherence, PEP initiation, PEP-to-PrEP transition, and repeat PEP use.

- PrEP initiation: the number of participants at each pharmacy that initiated (i.e., were dispensed) PrEP at the pharmacy or clinic **within 270 days** of initial pharmacy-based screening
- PrEP continuation:
 - The number of participants at each pharmacy that initiated PrEP at the pharmacy or clinic and returned to the pharmacy or clinic and refilled PrEP **within 270 days** of initial pharmacy-based screening (regardless of any gaps in pill coverage).
 - The number of participants at each pharmacy that initiated PrEP at the pharmacy or clinic and **refilled PrEP at least twice within 270 days** of initial pharmacy-based screening (regardless of any gaps in pill coverage).
 - The number of participants at each pharmacy that initiated PrEP at the pharmacy or clinic and refilled PrEP more than 7 days after their expected refill date (i.e., stopping and restarting, also referred to as “PrEP reinitiation”) **within 270 days** of initial pharmacy-based screening.
- PrEP adherence: The median adherence score (0-100) among participants at each pharmacy who initiated PrEP at the pharmacy or clinic –using the Wilson et al. scale (2020, *AIDS*)—as measured at **60 days** following initial pharmacy screening.
- PEP initiation: the number of participants at each pharmacy that initiated (i.e., were dispensed) PEP ≥ 1 times at the pharmacy or clinic within 3 days, as measured at **60 days** and **270 days** following initial pharmacy screening.
- PEP-to-PrEP transition: the number of participants at each pharmacy that successfully completed PEP (tested negative or self-reported testing negative for HIV between 28 and 45 days after initiating PEP at the pharmacy) **and** initiated PrEP at the pharmacy or clinic as measured at **60 days** and **270 days** following initial pharmacy screening.

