7.5.2 Secondary and tertiary outcomes

The analysis of the secondary outcomes of PrEP initiation within 270 days, any PrEP continuation within 270 days, at least 2 PrEP refills, any stopping and restarting PrEP, PEP initiation, PEP-to-PrEP transition, recurrent PEP use, PrEP/PEP initiation, PrEP/PEP continuation, PrEP adherence and the tertiary outcome of follow-up HIV testing will be similar to those described in Sections 7.5.1.1. Furthermore, the secondary analyses proposed in Section 7.5.1.3 will be performed for these outcomes (as appropriate for the outcome), with the exception of the secondary analysis investigating interactions. For the analysis of PrEP initiation with 270 days, the sensitivity analysis described in Section 6.7, in which PrEP initiation at 60 days is used to impute missing PrEP initiation at 270 days, will be performed.

For the exploratory outcome of PrEP coverage, descriptive statistics in each arm will be provided.

The tertiary outcomes (including acceptability, appropriateness, willingness to pay/charge, feasibility, and adaptations) will be summarized using descriptive statistics when assessed quantitatively and analyzed using a combination of inductive and deductive approaches (e.g., thematic content analysis) when assessed qualitatively. Similarly, the HIV risk behavior outcomes will be analyzed descriptively. No formal statistical comparisons will be performed for these tertiary outcomes.

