7.7 Post-unblinding update: December 16, 2025

The study team was unblinded to the results of the analysis on November 6, 2025 prior to the final DSMB meeting on November 13, 2025. The last version of this SAP, with all sections finalized with the exception of this post-unblinding update, was on November 5, 2025—prior to unblinding of any study team members. Summary statistics generated for the November DSMB meeting showed notable variability in completion of 60-day surveys across the 4 study arms. To understand the source of this heterogeneity, pharmacy data for the three intervention (i.e., non-SOC) arms were evaluated. These data indicated that a large number of individuals who did not complete the 60-day survey did in fact initiate/continue PrEP/PEP. This indicated that the planned outcome imputation approach, in which individuals who did not respond to the survey were assumed to have failed (i.e., not initiated/continued PrEP/PEP), likely did not reflect the nature of missingness. Following conversations with DSMB members and other experts, the study team decided to change the imputation approach.

The new imputation approach would impute PrEP/PEP outcomes for individuals who did not complete the survey using the proportion of PrEP/PEP initiations/continuations among individuals in the same pharmacy who did respond to the survey. Thus, if Pharmacy A enrolled 100 participants, 70 of whom responded to the survey and 14 of whom (20%) indicated they had initiated PrEP, then the PrEP initiation outcome for the 30 non-responders would be imputed as a binomial random variable with a success probability of 20%. As indicated above, evaluation of the pharmacy record data in the three intervention (i.e., non-SOC) arms indicated that the proportion of individuals who, per pharmacy records, initiated PrEP (for instance) was similar among those who did and did not complete the survey (42.8% and 40.5%, respectively). Thus, while the analysis based on the imputation procedure proposed in Section 6.7 will be reported in the main results manuscript as the pre-specified analysis, emphasis in that paper will be placed on the results from the analysis using the new imputation approach described in this paragraph, noting that this was not prespecified. We note that the decision to shift focus to this new imputation approach was made prior to seeing the results with the new imputation approach.

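### For cumulative 270-day secondary outcomes compared with standard of care, a missing day-270 status is scored as failure even when the day-60 survey already recorded the success.

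*SAP*

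**What the plan says.** **Outcomes.** SAP section 3 defines the 270-day secondary outcomes as events that have happened by then. PrEP continuation, for example, is a refill within 270 days "of initial pharmacy-based screening (regardless of any gaps in pill coverage". PrEP initiation, PEP initiation, the two transitions, recurrent PEP and the combined PrEP/PEP outcomes are also counted up to day 270.

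**Data.** Comparisons with SOC rest on self-report. Section 6.6 describes "brief surveys among all clients at 60 and 270 days post enrollment", so most participants have two chances to report an event.

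**Missing data.** Section 6.7 says of missing PrEP outcomes: "we will impute missing values as failures (i.e., did not initiate or did not continue, depending upon the outcome under consideration". It adds: "This same strategy will also be applied to our secondary PrEP/PEP outcomes".

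**Carry-forward.** Section 6.7 then adds a sensitivity analysis "where PrEP initiation at 60 days is used to impute missing PrEP initiation at 270 days". Its example reads "if a participant reports initiating PrEP at 60 days, but PrEP initiation status at 270 days is unavailable, we will consider this participant to have"; the sentence ends by counting that person as an initiator by day 270. Section 7.5.2 repeats this for PrEP initiation alone. No other 270-day outcome has such an analysis.

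**Post-unblinding rule.** The approach in section 7.7 "would impute PrEP/PEP outcomes for individuals who did not complete the survey using the proportion of PrEP/PEP initiations/continuations"; that proportion comes from responders at the same pharmacy. The section 6.7 analysis is still to be reported as the prespecified one.

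**The concern.** Someone dispensed PrEP by day 60 has, by the SAP's own definition, been dispensed PrEP within 270 days. The same holds for a first refill, a first PEP course, a completed transition or a second PEP course. Once the day-60 survey records one of these, the 270-day value is known and there is nothing to impute. The main rule nevertheless sets it to failure when the day-270 status is missing.

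The SAP's own layout supports this reading. If the main analysis already used the day-60 answer, the carry-forward sensitivity analysis would change nothing. The reason given for it is reduced recall bias, but what it mainly corrects is the misclassification of known successes.

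Two things are at stake:

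- **Coherence.** A cumulative count can go down over time.
- **Bias.** Under this rule each arm's expected count is multiplied by its day-270 response rate, so any difference in response between arms passes into the rate ratio. Section 7.7 reports marked differences between arms in completing the 60-day survey. The combined PrEP/PEP outcomes are called key secondary and tested at 0.0167 (sections 4.5 and 6.4), and section 3 defines them at 270 as well as 60 days.

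**Working it through.** **Inputs from SAP section 4.5.** Day-60 survey completion r60 = 0.75; initiation among completers p60 = 0.80; targets of 1,119 PrEP and 2,400 PEP initiations.

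**The plan's own figure.** Enrolment = target / (r60 × p60).

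- PrEP candidates: 1,119 / 0.60 = 1,865
- PEP candidates: 2,400 / 0.60 = 4,000
- Total: 5,865, as stated in the SAP

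**Assumptions, not in the SAP.** Day-270 response r270 varies from 50% to 80%; response at day 270 is independent of response at day 60; cumulative initiation p270 is as stated in each step.

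**Formulas for N = 1,865 PrEP candidates.**

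- 60-day count: N × r60 × p60 = 1,865 × 0.75 × 0.80 = 1,119
- 270-day count with missing scored as failure: N × r270 × p270
- Recorded day-60 initiators scored as 270-day failures: 1,119 × (1 − r270)
- 270-day count with carry-forward and no new initiation: N × p60 × [1 − (1 − r60)(1 − r270)]
- p270 needed for the 270-day count to equal the 60-day count under the current rule: 0.60 / r270

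The two count columns take no new initiation after day 60 (p270 = 0.80).

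| r270 | Day-60 initiators recoded as failures | 270-day count, current rule | 270-day count, carry-forward | p270 needed to equal 1,119 |
|---|---|---|---|---|
| 50% | 560 | 746 | 1,306 | not attainable |
| 60% | 448 | 895 | 1,343 | 100% |
| 65% | 392 | 970 | 1,361 | 92.3% |
| 70% | 336 | 1,044 | 1,380 | 85.7% |
| 75% | 280 | 1,119 | 1,399 | 80.0% |
| 80% | 224 | 1,194 | 1,417 | 75.0% |

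The current rule gives a 270-day count below the 60-day count whenever r270 × p270 < 0.60. Carry-forward cannot do so.

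A fall is not certain. At r270 = 70% with 10 percentage points of new initiation, the current rule gives 1,865 × 0.70 × 0.90 = 1,175, above 1,119.

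A stable total can also hide the error. At r270 = 75% the total is unchanged at 1,119 only because the 280 known initiators lost are replaced by day-60 non-responders reached at day 270: 1,865 × 0.80 × 0.25 × 0.75 = 280.

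**Effect on a rate ratio.** This is the ratio of the two arms' ascertainment of initiators by day 60. All response rates are assumed, response is independent, and those still unknown count as failures.

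| Day-60 response | Day-270 response | Current rule | Either survey |
|---|---|---|---|
| 75% / 75% | 85% / 65% | 0.85/0.65 = 1.31 | 0.9625/0.9125 = 1.05 |
| 85% / 65% | 85% / 65% | 1.31 | 0.9775/0.8775 = 1.11 |
| 85% / 65% | 75% / 75% | 1.00 | 0.9625/0.9125 = 1.05 |

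**The case against.** **The issue is secondary, and partly covered already.** Both primary outcomes are 60-day outcomes, and the power figures in Table 4 do not depend on day-270 data. For PrEP initiation the coherent analysis is prespecified, though only as a sensitivity analysis. This stands and limits the severity. It does not help the other cumulative outcomes, which have no carry-forward analysis.

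**The size rests on assumptions.** The 75% is a day-60 planning figure, and the 85% and 65% are invented. People who answered at day 60 may be more likely to answer again, which would make the loss smaller than 280 to 448. This stands; the figures are illustrations.

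**A reader might infer that every 270-day rate ratio is biased.** The SAP does not support that. Comparisons among Arms 1-3 use pharmacy records (section 7.5.1.3, extended by 7.5.2). In the SOC comparisons, losing the same share of successes in each arm leaves the ratio unchanged. Bias needs day-270 response to differ by arm, and the SAP reports such differences only for day 60.

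**A reader might also infer that section 7.7 repeats the error.** Its text discusses the 60-day survey and does not say that the new rule covers day 270. If it does, a known day-60 success could be redrawn as a failure. If it does not, the section 6.7 rule remains for day 270. This is an ambiguity to settle, not a demonstrated error.

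**Changing the rule has a cost.** The team was unblinded on 6 November 2025, so replacing a prespecified rule and dropping its results would be hard to defend. Carry-forward also brings day-60 response differences into the 270-day outcome (last row of the second table, 1.00 to 1.05). Both points stand and shape the remedy.

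**Conclusion.** The concern holds for the survey-based comparisons with SOC on cumulative 270-day secondary outcomes. Section 6.7, read with the definitions in section 3, recodes known successes as failures, and nothing elsewhere in the SAP repairs this in the main analysis. The gap is fully open for any PrEP continuation, PEP initiation, PEP-to-PrEP and PrEP-to-PEP transition, recurrent PEP and the combined PrEP/PEP outcomes. The outcome of at least two refills is affected only where both refills were already recorded at day 60.

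The misclassification follows from the text. Its size does not: 280 to 448 of 1,119 day-60 initiators corresponds to assumed day-270 response of 75% down to 60%, independent of day-60 response. A 270-day count below the 60-day count is possible, not certain, and bias in the SOC rate ratios is conditional on differential day-270 response. Severity: should-fix.

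**What to change.** 1. In sections 6.7 and 7.5.2, score every cumulative 270-day outcome as a success if the event was reported at either survey. Impute only participants still undetermined after both surveys.
2. In section 7.7, state whether the new imputation applies at day 270. If it does, state that it never overrides a success recorded at day 60.
3. Date the change, label it not prespecified, and still report the section 6.7 analysis and its PrEP-initiation sensitivity analysis, in line with how section 7.7 treats its own change.
4. Report survey response by arm at both time points, so that readers can judge any remaining distortion.

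**Cost.** A few sentences and a re-run on data already held. The disadvantages are one more post-unblinding change and some carry-over of day-60 response differences, about 1.05 in the illustration. The rule also resolves a day-60 success followed by a day-270 denial in favour of success; the number of such participants should be reported.
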